4.3 Toxicity Management and Dose Delays or Modifications

Any patient who receives an injection of NSC-CRAd-S-pk7 will be evaluable for toxicity endpoints. In the event that the final pathology reading reveals anything other than a malignant glioma, the patient will be removed from the protocol but will continue to be followed for toxicity. Such a patient will not be counted as one of the minimum number required without DLT for advancement to the next dose level but will be counted if a DLT is experienced. Each patient will be assessed for the development of toxicity according to the timeframe referenced in the Schedule of Events table. Treatment all toxicity events, based on CTCAE v4.03 criteria, will be managed according to institutional guidelines.

There will be no dose delays or modifications as this is a single-dose therapy.

4.4 Study Product Administration

Arm A – Unresectable Patients

The patient will be brought to the operating room following an MRI. Biopsy coordinates will then be selected. Biopsy coordinates will consist of one to three sites; however, the neurosurgeon may elect to select as many as needed to obtain diagnosis, as is done with standard neurosurgical practice. Target infusion coordinates will consist of one to three sites within areas of tumor selected by the neurosurgeon. These can be the same or different from the biopsy coordinates. The scalp will be prepped and draped in the usual sterile fashion. After the application of local anesthesia, an incision is made and the skull is exposed. A single burr hole is drilled and, after opening the dura mater and underlying pia, the brain is penetrated with a standard stereotactic needle down to the biopsy coordinates. After frozen tissue confirmation of the presence of malignant glioma, a syringe is filled with up to 1 ml of the appropriate dose of NSC-CRAd-S-pk7. This syringe is attached to a fresh, disposable stereotactic needle. Slowly, 0.5 ml is injected into the stereotactic needle to fill its dead space and the needle is then capped. This operation will be performed on a sterile table that is separate from the main OR and patient tables. The stereotactic needle and syringe are then reinserted into the stereotactic frame and advanced to the target infusion coordinates which will be selected by the surgeon to avoid injections into adjacent motor or speech cortex, the cerebral ventricle, or spillage into the subarachnoid space. Up to 1 ml of NSC-CRAd-S-pk7 is then infused slowly over a period of approximately three to seven minutes. This will require infusion of a chaser of about 0.5 ml of saline (sterile, non-bacteriostatic) into the needle to push the last 0.5 ml of NSC-CRAd-S-pk7 out of the dead space of the stereotactic needle. The needle is then left in place for an additional three to seven minutes before withdrawal. Standard neurosurgical techniques will then be used to close the surgical wound. Staples will not be used due to interference with simulation for radiation therapy.

Arm B – Resectable or partially resectable

A craniotomy with resection of the tumor will be performed. At the neurosurgeon's discretion, this may involve stereotactic methods and/or intraoperative navigational guidance and/or intraoperative MRI or other radiologic guidance. Tumor resection will be performed per routine. After the tumor resection has been completed, freehand injections of 100 microliters of the NSC-CRAd-S-pk7 virus will be performed by the neurosurgeon into up to ten sites in the wall of the resection cavity. The total dose of the NSC-CRAd-S-pk7 will be determined by the appropriate dose escalation scheme. The sites will be at least 1 cm apart and will be selected by the surgeon to avoid injections into adjacent motor or speech cortex, the cerebral ventricle, or spillage into the subarachnoid space. After the injections are completed, the remainder of the operation will consist of routine wound closure.

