4.1 Overview

This study is an open label, Phase I, dose-escalation gene therapy clinical trial with two arms:

1. **Arm A** – Unresectable disease, will receive stereotactic intratumoral injection of NSC-CRAd-S-pk7 immediately following stereotactic biopsy confirmation of clinical diagnosis
2. **Arm B** – Resectable or partially resectable disease, will receive injection of NSC-CRAd-S-pk7 into remaining tumor or tumor bed after resection.

Pathologic confirmation of a malignant glioma must be made at the time of surgery prior to injection. If this is not possible, the injection will not be performed and the patient will no longer be eligible for the study. In the event that the final pathology reading reveals anything other than a malignant glioma, the patient will be removed from the protocol but will continue to be followed for toxicity. Patients having not received any study treatment will need to be replaced and will not be counted as one of the minimum number required without DLT for advancement to the next dose level but will be counted if a DLT is experienced.

Standard radiotherapy and chemotherapy will begin 10-14 days after NSC-CRAd-S-pk7 injection. Long-term follow-up of general health status and any side effects may continue for life. This will be done by telephone contact or letter with the patient or their primary care physician. Medical records will also be reviewed to assess for any potential side effects and for general health status.

An attempt will be made to perform a complete autopsy on any patient who dies, if consent is given by the legally authorized representative. In addition to standard pathological examinations, tissues will be taken for additional studies such as analysis of CRAd-S-pk7 presence and expression.

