4.8 Duration of Therapy

Within 28 days of screening, patients will receive a one-time intratumoral injection of NSC-CRAd-S-pk7 during the resection or biopsy procedure, at the dose specified in the dose-escalation protocol. Patients will remain inpatient for standard of care post-operative procedures, including an MRI of the brain. Discharge will take place when clinically appropriate.

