8.1.5 Protocol dose specifics

One ml given as a one-time dose.

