10.2 Sample Size and Accrual

This phase 1 study is not powered to detect statistically significant differences in efficacy. The primary endpoint of this Phase I dose-escalation study is the MTD of NSC-CRAd-S-pk7 when administered with standard radiation and chemotherapy in patients with malignant glioma. The 3+3 design has a 71% chance (49%, 17%) of dose escalating when the true toxicity rate for that dose is 20% (30%, 50%).

If all three dose levels are administered, the minimum number of patients enrolled will be 9 per arm and the maximum number of patients will be 18 per arm, for total accrual of 18-36 patients enrolled. Based upon the dose escalation schema described, groups of three to six patients will be entered at a dose level in each arm. Using this algorithm, the probabilities of dose escalation for various true DLT rates are given in Table 10. For example, if the true DLT is 50% at a dose level, there is a 17% chance that the dose would be escalated. The maximum tolerated dose determined in this study will be the recommended dose for a Phase II study. In the event the final pathology reading reveals anything other than a malignant glioma, such a patient will not be counted as one of the minimum number required without DLT for advancement to the next dose level but will be counted if a DLT is experienced.

Table 10– Probabilities of Dose Escalation	
20%	71%
30%	49%
40%	31%
50%	17%
60%	8%

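### The DLT counting rules set no minimum delivered dose, so a part-dosed glioma patient without a DLT counts in full at the assigned level

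*Combined protocol and SAP*

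**What the plan says.** **Dose.** Table 1 (section 4.2) sets three levels: 5.0x10^7, 1.0x10^8 and 1.5x10^8 cells (6.25x10^10, 1.25x10^11 and 1.875x10^11 vp). Section 4.8 has each patient injected once "at the dose specified in the dose-escalation protocol". Section 8.1.5 gives the volume: "One ml given as a one-time dose". Section 4.3, under toxicity management, adds: "There will be no dose delays or modifications as this is a single-dose therapy".

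**Delivery.** For Arm B, section 4.4 states that "freehand injections of 100 microliters of the NSC-CRAd-S-pk7 virus will be performed by the neurosurgeon into up to ten sites" in the cavity wall. It also states: "The sites will be at least 1 cm apart and will be selected by the surgeon to avoid injections into adjacent motor or speech cortex", and the ventricle and subarachnoid space are to be avoided too. It ties the total dose to the escalation scheme, but sets no minimum number of sites and does not say whether a site may be injected twice. For Arm A, it allows an infusion of at most 1 ml, again with no minimum.

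**Counting.** Section 4.3: "Any patient who receives an injection of NSC-CRAd-S-pk7 will be evaluable for toxicity endpoints". Two groups are kept out of the DLT-free count. The first is untreated patients (section 4.1: "Patients having not received any study treatment will need to be replaced"). The second is patients whose final pathology is not malignant glioma (sections 4.3 and 10.2: "such a patient will not be counted as one of the minimum number required without DLT for advancement to the next dose level"); they are counted if they have a DLT. The NOTE to Table 2 requires six patients treated at a level before it can be declared the MTD. It does not say what treated means when delivery is incomplete.

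**The concern.** A 3+3 rule clears a level on three or six patients, so each DLT-free patient carries much weight. The count should describe the toxicity of the level's own dose. Ten sites of 100 microliters make exactly 1 ml, so Arm B has no slack: each site that the surgeon cannot use removes a tenth of that volume. The dose steps are only 2-fold and 1.5-fold, so a moderate shortfall can wipe out the difference between adjacent levels.

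Applied as written, the rules could then clear a level, or meet the six-patient MTD requirement, partly on patients who received no more than the dose below. The MTD is the primary endpoint and becomes the recommended Phase II dose (section 10.2).

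**Working it through.** **1. The plan's own figure.** With a common DLT rate p, P(escalate) = (1-p)^3 + 3p(1-p)^2 x (1-p)^3. At p = 20, 30, 40, 50 and 60% this gives 70.9, 49.4, 30.9, 17.2 and 8.2%. Table 10 states 71, 49, 31, 17 and 8%, so it is reproduced. It assumes that all patients counted at a level share one DLT rate.

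**2. Delivered dose, main assumption.** The assigned cells are in 1 ml at every level (section 8.1.5) and each usable site gets one 100-microliter injection. Delivered dose = sites/10 x assigned dose.

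| Sites | Level 2 cells | Level 3 cells |
|---|---|---|
| 10 | 1.0x10^8 | 1.5x10^8 |
| 9 | 9.0x10^7 | 1.35x10^8 |
| 8 | 8.0x10^7 | 1.2x10^8 |
| 7 | 7.0x10^7 | 1.05x10^8 |
| 6 | 6.0x10^7 | 9.0x10^7 |
| 5 | 5.0x10^7 | 7.5x10^7 |

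Five sites at level 2 equal level 1 (5.0x10^7 cells, 6.25x10^10 vp). Six sites at level 3 give 9.0x10^7 cells and 1.125x10^11 vp, below level 2. The delivered dose equals the level below at 5.0x10^7/1.0x10^8 = 50% (level 2) and 1.0x10^8/1.5x10^8 = 67% (level 3).

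**3. Delivered dose, alternative assumption.** Suppose the concentration is fixed at 1.5x10^8 cells/ml and volume rises with level. Level 2 then needs 1.0/1.5 = 0.67 ml, about seven sites. Five sites give 0.5 x 1.5x10^8 = 7.5x10^7 cells, 75% of level 2 and still above level 1. Level 3 still needs ten sites, so its column is unchanged.

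**4. Effect of replacing DLT-free part-dosed patients.** Put one part-dosed patient, with DLT rate q, among the first three; everyone else has rate p. If that patient is DLT-free, a full-dose patient takes the place. The slot then registers a DLT with probability s = 1 - (1-q)(1-p), and P(escalate) = (1-s)(1-p)^2 + [s(1-p)^2 + (1-s)2p(1-p)] x (1-p)^3.

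- p = q = 20%: s = 0.36. 0.4096 + 0.4352 x 0.512 = 63.2%, against 70.9%.
- p = q = 30%: s = 0.51. 0.2401 + 0.4557 x 0.343 = 39.6%, against 49.4%.
- p = 30%, q = 15%: s = 0.405. 0.2916 + 0.4484 x 0.343 = 44.5%. Counting that patient in full instead gives 0.4165 + 0.4305 x 0.343 = 56.4%. With all patients fully dosed it is 49.4%.

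The values of q are illustrations; the documents give no DLT rate by delivered dose.

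**The case against.** **A default exists.** A reader might infer that no rule covers a part-dosed patient. That goes too far. Section 4.3 makes every injected patient evaluable for toxicity, and only two groups are excepted, so the default is to count at the assigned level. Section 4.3 does distinguish being evaluable from being counted as DLT-free, so this default is itself read from the rules together. The gap is that the default carries no minimum-dose condition.

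**Full delivery is inferred.** A reader might also infer that the protocol expressly requires the whole dose, making any shortfall a deviation. No sentence says so. Sections 4.4, 4.8 and 8.1.5 show that the assigned dose is intended, but the statement in 4.3 concerns toxicity management. If repeat injection at a site is allowed, there need be no shortfall in Arm B.

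**The arithmetic depends on a preparation SOP (Appendix B) that is not in the text.** This stands, and is why step 3 gives a second case.

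**Spacing seldom limits.** On an idealised spherical cavity, ten sites 1 cm apart fit from a diameter of about 1.8 cm using the whole wall, or about 2.2 cm using half. Spacing alone therefore binds only in small cavities. Avoiding eloquent areas may remove further sites, by an unknown number.

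**Oversight exists.** The DMC reviews safety before each higher level (4.2.1), data in the DLT period are submitted weekly (11.4), and deviations are reported (11.6.2). These may reveal a shortfall but do not change how it is counted. Because fewer than ten sites are permitted, a shortfall may not be seen as a deviation at all.

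**The remedy has its own bias.** This stands: step 4 shows a loss in escalation probability that is not trivial.

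**Conclusion.** The point holds in this form: the counting rules have no minimum-delivered-dose condition, while section 4.4 lets delivery fall short in both arms. Any injected glioma patient without a DLT therefore counts in full by default. With the assigned cells in 1 ml and one injection per site, five of ten sites at level 2 match level 1, and six of ten at level 3 fall below level 2. If volume rises with level, the level 2 shortfall is smaller and the level 3 result is unchanged.

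A reader might go on to infer that the MTD will be set too high. The documents do not support that: they give neither the frequency of part-dosing nor DLT rates by delivered dose. If DLT risk is flat over this range, counting part-dosed patients has no effect on escalation. This is an inexpensive improvement to the rule that decides the primary endpoint, held with medium confidence; it does not invalidate the design.

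**What to change.** 1. Record the volume and cells delivered for each patient in both arms, and the number of sites in Arm B.
2. Extend the rule in 4.3 and 10.2. A patient who receives less than a pre-stated fraction of the assigned cells is not counted as DLT-free and is replaced, but is counted if a DLT occurs. The fraction is the sponsor's choice but should be well above 67%, for example 80-90%. Apply the same definition to the six patients in the NOTE to Table 2.
3. Give the DMC the delivered dose beside the DLTs before each escalation decision.
4. State in 4.4 what the surgeon does when fewer than ten sites are usable. Spreading 1 ml over fewer sites raises the volume at each: 1000/8 = 125 microliters, or 1000/5 = 200, double the stated amount. That should be allowed only if the sponsor judges it safe near the structures 4.4 protects.

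**Cost.** A short amendment, and delivered-dose fields on the CRF if not already there. There will be occasional replacements. If all three levels already need six patients, these take an arm above 3 x 6 = 18. The rule is also conservative, because part-dosed patients count only when they have a DLT; step 4 of the working gives the size. The protocol already accepts this for non-glioma patients, and the amendment should state it openly.

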4.5 Planned Duration of Therapy

Based on projections from current clinical practice, it is anticipated that the accrual will take 12-18 months to complete.

4.6 Concomitant and Adjuvant Medications/Treatments

4.6.1 Peri-Operative Medications

- Antibiotics: All patients will receive a single intravenous dose of cefazolin, or the antibiotic defined by standard care just prior to the surgical procedure.
- Steroids: If clinically indicated, patients may receive dexamethasone prior to and/or following viral injection.
- Anticonvulsant: Anticonvulsant therapy will be administered according to the usual neurosurgical guidelines.
- Analgesics: Pain medication may include codeine and small doses of other narcotic medications.

4.6.2 Radiation Therapy

Radiation will be determined and administered as per standard of care for the patient. It will start 10-14 days after NSC-CRAd-S-pk7 injection. It will consist of standard external field radiation, limited to the area of tumor and brain adjacent to tumor, fractionated at doses of 200 cGy per day for approximately six weeks to a total of 5500-6000 cGy.

4.6.3 Chemotherapy

Standard of care TMZ will be administered concurrent with radiotherapy (75mg/m²). Patients will sign a drug calendar daily indicating that they have completed the daily TMZ dose during the XRT/TMZ phase (weeks 2 through 7).

Four weeks later, TMZ will be given (150mg/m² for the first cycle then escalated in the absence of > grade 1 hematotoxicity to 200mg/m² if tolerated) during each cycle for a total of 6 cycles. A cycle will consist of 5 days “on”/23 days “off” per Stupp protocol. Dose delays or modifications will be according to the literature at the discretion of the treating oncologist as this is a standard of care treatment.

4.7 Other Modalities or Procedures

Tumor resection or biopsy surgery is a standard of care procedure that will follow Northwestern Medicine institutional guidelines. The tissue collected during surgery will undergo testing to confirm diagnosis and for research purposes, however any other procedures related to surgery are standard of care.

4.8 Duration of Therapy

Within 28 days of screening, patients will receive a one-time intratumoral injection of NSC-CRAd-S-pk7 during the resection or biopsy procedure, at the dose specified in the dose-escalation protocol. Patients will remain inpatient for standard of care post-operative procedures, including an MRI of the brain. Discharge will take place when clinically appropriate.

4.9 Duration of Follow Up

Patients will have a follow-up visits days 1-3 while hospitalized, days 7, 14, and 28 after NSC-CRAd-S-pk7 administration and then at day 56, and every 8 weeks after until disease progression or patient withdrawal. They will be monitored for toxicities by physical exam and laboratory results through day 56. They will also undergo a brain MRI on day 28 and at day 56 to monitor for toxicity and disease progression, then every 8 weeks to monitor for disease progression. Survival status will be monitored until patient death or for up to 5 years.

4.10 Removal of Subjects from Study Treatment and/or Study as a Whole

Patients can be taken off the study treatment and/or study as a whole at any time at their own request, or they may be withdrawn at the discretion of the investigator for safety, behavioral or administrative reasons. The reason(s) for discontinuation must be clearly documented on the appropriate eCRF and may include:

- Patient voluntarily withdraws from treatment (follow-up data collection permitted)
- Patient withdraws consent (no follow-up data collection permitted)
- Patient is unable to comply with protocol requirements
- Patient demonstrates disease progression
- Patient experiences unacceptable toxicity
- Treating physician determines that continuation on the study would not be in the patient's best interest
- Patient becomes pregnant
- Patient develops a second malignancy that requires treatment which would interfere with this study
- Inability to participate in the medical decision making process.

- New medical information which may adversely affect the health of the patient in the context of the trial.

Long-term follow-up of general health status and any side effects may continue for life after removal from study treatment. Follow-up will be done by telephone contact or letter with the patient, family member, or their primary care physician. Medical records will also be reviewed to assess for any potential side effects and for general health status.

5.0 STUDY PROCEDURES

All patients will undergo all standard of care and clinically indicated evaluations in addition to any study specific evaluations. **Table 3** presents a summary sample schedule. **Table 4** outlines the treatment evaluation schedule. **Table 5** presents the entire study calendar.

Table 3– Sample Schedule	
Screening	
Day -28 until Day -1	Informed consent, medical history and physical exam. baseline laboratory assessments, MRI
Week 1	
Day 0	Intratumoral injection of NSC-CRAd-S-pk7
Days 6-7 (+ 3days)	Simulation for RT
Week 2-7	
Days 1-7 (+ 3days)	RT (1.8-2 Gy) (Days 1-5 only) TMZ (75 mg/m ²)
Week 12	
5 Days on/23 Days off	TMZ (150-200mg/m ²)

Table 4 – Treatment Evaluation Schedule	
History, Physical Exam	≤ 7 Days from Day 0 Weekly 2-4 weeks after completion of XRT At least every three months for first year Annually for five years
Quality of Life questionnaire (FACT-Br version 4) and mini-mental status exam	≤ 7 Days from Day 0 Once during RT administration (week 2 or 3) 2-4 weeks after completion of RT Every three months for the first year or until disease progression
CBC, platelets, PT, PTT, serum electrolytes, creatinine, liver function tests-AST, ALT and bilirubin	≤ 7 Days from Day 0 Weekly during administration (weeks 2, 4, and 6) Annually for five years (CBC Count)
Blood collection for immune research studies*	≤ 7 Days from Day 0 (may be collected in week 2-3 after the NSC-CRAd injection and 2-4 weeks after completion of RT)
Blood collection for RCR testing*	≤ 7 Days from Day 0, 3 months, 6 month, and one year, then annually
Urine/serum pregnancy test (if applicable)	≤ 7 Days from Day 0
Brain MRI	≤ 21 Days from Day 0 2-4 weeks after completion of RT

	Every two-three months for the first year or until disease progression Annually for five years
--	---

Table 5. Activities	Screening	Study Drug Administration Period							Follow-up Period			
	Day -28 to -1	Day 0	Day 1	Day 2	Day 3	Day 7	Day 14	Day 28	Day 42	Day 56, every 8 weeks thereafter	Yearly	
Clinical Assessments												
Informed Consent	X											
Medical/Cancer History	X											
Physical Exam /targeted neurological exam	X	X	X	X	X	X	X	X		X		X
KPS	X	X						X	X		X	X
Height (only at Screen) and Weight	X					X	X	X				
Vital Signs	X	X	X	X	X	X	X	X				
Adverse Events	X	X	X	X	X	X	X	X		X		
Concomitant Meds	X	X	X	X	X	X	X	X			X	
Quality of Life Measures	X						X				X ³	
Clinical Laboratory												
Urine or serum Pregnancy test	X	X										
Hematology Panel ⁴	X	X		X	X	X	X	X	X		X	
Coagulation Panel ⁴	X	X			X	X	X					
Serum Chemistry Panel ⁴	X	X		X	X	X	X	X	X		X	
Urinalysis with microscopy	X	X					X					
ECG	X	X			X		X					
Registration	X											
Study Drug Administration												
Surgery			X									
NSC-CRAd-S-pk7			X									
Blood/Tissue Testing and Imaging												
Serum Cytokine profile			X			X	X	X	X			
Immune Function blood sample			X				X	X	X			
RCR testing ⁵	X									X		X
Viral Shedding	X				X							
MRI Scans	X			X				X		X		X
Tumor Sample			X									
CSF Sample			X									

¹Hematological and metabolic toxicities assessed at week 2, 4, and 6 ²If available ³every 8 weeks up to one year⁴Hematology panel- complete blood count with differential and platelet count; Coagulation panel- prothrombin time/International normalized ratio, partial thromboplastin time; Chemistry panel- glucose, blood urea nitrogen, creatinine, eGFR, sodium, potassium, calcium, chloride, bicarbonate, total bilirubin, alkaline phosphatase, SGOT, SGPT, total protein, albumin; ⁵Baseline, day 90(+/- 14 days), 6 months, 1 year, then annually

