- CBC, platelets, creatinine, AST, ALT, and bilirubin will be monitored bi-weekly during administration (weeks 2, 4, and 6).
- Blood for immune research studies* (10 to 40 cc) may be collected in week 2-3 after the NSC-CRAd injection and 2-4 weeks after completion of radiation therapy
- MRI of the brain approximately 28 days after study product injection, 2-4 weeks after completion of radiation, and then every 2-3 months for the first year or until disease progression.
- If surgery is performed, tumor samples will be examined in conjunction with the pathologist and samples retained for future studies if consent given by the patient.
- Evaluation once a year for 5 years. Evaluations will include: Physical and neurological examination, MRI, and CBC with differential count.

Statistical Considerations:

Statistical analysis will be descriptive only, with no hypothesis testing. All the endpoint data will be collected and described in summary tables for both two arms at each dose. In general, descriptive statistics (n, mean, standard deviation, median, minimum, and maximum) will be presented for continuous variables. Frequencies and percentages will be calculated for categorical and ordinal variables at each category. All study data will be presented in by-subject data listings. Statistical analyses will be performed using SAS9.4 (SAS Institute Inc., Cary, NC).

The maximum tolerated dose (MTD) will be determined according to the dose escalation algorithm. If >2 patients do not complete the initial RT/TMZ phase or rule if > 2 patients experience life threatening or fatal neurologic toxicity, the trial will be stopped to analyze, in conjunction with the DMC, whether this regimen is tolerable.

Demographic (age, sex, height and weight) and baseline disease characteristics (including baseline KPS), will be summarized for both arms as well as the entire group. Kaplan-Meier curves and median survival estimates with confidence limits will be given for both overall survival and progression-free survival. The association of extent of immune response with overall survival will be determined by Cox's proportional hazards model.

Safety parameters will be analyzed descriptively, and presented in standard frequency tables (adverse events), shift tables (Laboratory parameters) and summaries of change from baseline over time (vital signs, physical examination, ECG and laboratory parameters).

Sponsor/Licensee:

Northwestern University/[name]

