4.2.1 Definitions of Dose-limiting Toxicities

- Subjects will be evaluated for dose-limiting toxicities (DLT period) from the time of signing informed consent through completion of concomitant radiation and temozolomide.
 - DLTs will be evaluated using CTCAE v 4.03 criteria
 - The DLT will be defined as any of the following:
 - Toxicity attributed to study product
 - Any grade 3 toxicity including hematologic and non-hematologic toxicities
 - Any grade 3 toxicity related to the intervention requiring interruption or delay in radiation therapy for more than seven days except CNS hemorrhage*
- * Grade 3 (asymptomatic) radiologic evidence of CNS hemorrhage (commonly seen after biopsy) is not a DLT. Grade 4 (symptomatic) CNS hemorrhage is a DLT. Assessment of neurological toxicity relates to the relative changes from the pre-treatment neurological status. Other anticipated toxic phenomena that are not related directly to viral transduction of the brain tumor or neurological complications which can be explained by the presence of the mass lesion and are compatible with the natural history of malignant brain tumors may require cessation of treatment in individual patients. Such occurrences would not be considered DLT unless they occur with a greater frequency than expected in this patient population.
- A safety analysis will take place 14 days after the first and second subjects receive treatment, and before moving to the next higher viral dose level. The DMC will assess the safety of administering NSC-CRAd-S-pk7 in future patients either at the same dose or a modified dose. No patients will receive treatment until the DMC provides their recommendation.
 - The maximally tolerated dose is defined as the dose level immediately below the dose where the DLT was observed.

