7.1 Adverse Event Monitoring

Adverse event data collection and reporting, which are required as part of every clinical trial, are done to ensure the safety of subjects enrolled in the studies as well as those who will enroll in future studies using similar agents. Adverse events are reported in a routine manner at scheduled times during a trial (from screening through the Day 56 visit). In addition, certain adverse events must be reported in an expedited manner to allow for optimal monitoring and patient safety and care.

All patients experiencing an adverse event, regardless of its relationship to study drug, will be followed until:

- the adverse event resolves or the symptoms or signs that constitute the adverse event return to baseline;
- any abnormal laboratory values have returned to baseline;
- there is a satisfactory explanation other than the study drug for the changes observed; or
- death.

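### Toxicity monitoring and routine AE reporting stop at Day 56, but the DLT window runs to completion of RT/TMZ, which in longer or interrupted courses can be later

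*Combined protocol and SAP*

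**What the plan says.** Section 4.2.1 opens the DLT window at informed consent and runs it "through completion of concomitant radiation and temozolomide". No calendar day is attached. Its list of DLTs includes "Any grade 3 toxicity including hematologic and non-hematologic toxicities", and also related grade 3 toxicity "requiring interruption or delay in radiation therapy for more than seven days".

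Safety collection is set by the calendar instead. On patients after injection, Section 4.9 says: "They will be monitored for toxicities by physical exam and laboratory results through day 56". Section 7.1 sets routine adverse-event reporting "from screening through the Day 56 visit".

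The on-treatment blood tests appear in Table 4 as "Weekly during administration (weeks 2, 4, and 6" and in the Study Summary as "will be monitored bi-weekly during administration (weeks 2, 4, and 6". After these, the same Table 4 row lists only "Annually for five years (CBC Count". Table 3 runs RT/TMZ through week 7.

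On the length of treatment:
- Section 4.6.2 starts radiotherapy 10 to 14 days after injection and gives 200 cGy per day for about six weeks, to a total of 5500-6000 cGy.
- Table 3 allows fractions of 1.8-2 Gy, five days a week.
- Section 8.2 (protocol dose specifics for temozolomide) allows concomitant dosing for up to 49 days.
- Sections 4.6.3 and 8.2 leave temozolomide delays to the treating oncologist.

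**The concern.** The DLT window closes on an event, and data collection closes on a date. Nothing in the protocol links the two. If RT/TMZ finishes after Day 56, the patient is still at risk of a DLT, but the stated laboratory monitoring and routine adverse-event reporting have ended.

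This bears on the primary endpoint, because DLT counts drive every decision in Table 2. Grade 3 hematologic toxicity is found only by a blood test, whether or not it must also be attributed to the study product. Section 8.2 lists lymphopenia, thrombocytopenia, neutropenia and leukopenia among the common grade 3-4 abnormalities with temozolomide. In a cohort of three, one missed DLT turns 1 of 3 into 0 of 3, and the dose is then escalated without the three further patients that Table 2 would require.

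**Working it through.** **Inputs.** Start of RT/TMZ on Day 10-14 and total dose 5500-6000 cGy (4.6.2); fraction size 1.8-2 Gy, five days a week (Table 3); temozolomide for up to 49 days (8.2); collection limit Day 56 (4.9, 7.1). Injection is Day 0.

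**The plan's own figure.** 5500/200 = 27.5, so 28 fractions, and 28/5 = 5.6 weeks. 6000/200 = 30 fractions, and 30/5 = 6.0 weeks. This agrees with the stated six weeks or so.

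**Whole fractions within 55-60 Gy.** At 2 Gy: 28 to 30 (56-60 Gy). At 1.8 Gy: 31 to 33 (55.8-59.4 Gy). 34 x 1.8 = 61.2 Gy exceeds the cap and is left out.

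**Formula.** Last day = start day + span, where the span covers (fractions - 1) weekday steps.
- 30 fractions: 29 steps = 5 full weeks (35 days) + 4 weekdays. The span is 39 days from a Monday start. From any other weekday the last steps cross a weekend, giving 41.
- 33 fractions: 32 steps = 6 full weeks (42 days) + 2 weekdays. The span is 44 days from a Monday to Wednesday start and 46 from a Thursday or Friday start.

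Five start days by five weekdays give 25 calendar combinations. Missed fractions are made up on the next available weekdays. An interruption adds its full calendar length.

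| Course | Span (days) | Last day | After Day 56 |
|---|---|---|---|
| 28 x 2 Gy | 37-39 | 47-53 | 0 of 25 |
| 30 x 2 Gy | 39-41 | 49-55 | 0 of 25 |
| 31 x 1.8 Gy | 42 | 52-56 | 0 of 25 |
| 32 x 1.8 Gy | 43-45 | 53-59 | 7 of 25 |
| 33 x 1.8 Gy | 44-46 | 54-60 | 14 of 25 |
| 30 x 2 Gy, 1 missed fraction | 42 | 52-56 | 0 of 25 |
| 30 x 2 Gy, 2 missed fractions | 43-45 | 53-59 | 7 of 25 |
| 30 x 2 Gy, 7-day interruption | 46-48 | 56-62 | 24 of 25 |
| Temozolomide, 42 days | 41 | 51-55 | 0 of 5 start days |
| Temozolomide, 49 days | 48 | 58-62 | 5 of 5 start days |

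The planned 2 Gy course is inside the limit in every combination. Two missed fractions are the fewest that can take it past Day 56. Among uninterrupted courses the latest end is Day 62, which is 62 - 56 = 6 days past the limit. If temozolomide stops with radiotherapy instead, the latest is Day 60, which is 4 days past.

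The counts are calendar combinations, not probabilities. If every course starts on a Monday, 33 x 1.8 Gy ends on Day 54-58 (2 of 5 start days after Day 56), and 30 x 2 Gy with a seven-day interruption ends on Day 56-60 (4 of 5).

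**The case against.** The strongest reply is that the planned regimen is covered and that several duties already follow the DLT window:
- Section 4.2.1 says patients are evaluated for DLTs to the end of RT/TMZ and requires data monitoring committee review before the next dose level.
- Section 11.4 requires weekly data submission during the DLT period.
- Table 4 lists weekly history and physical examination.
- Section 8.2 directs blood-count and liver-function monitoring on temozolomide.
- Section 7.3.2 requires reporting of agent-attributed events after 56 days.

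These safeguards are real and make a missed event less likely. They do not close the gap. Data submission and committee review can use only what was collected, and none of these provisions fixes a blood test at the end of the window. The columns of Table 5 are broken in the text available, so it is not relied on. If it does place hematology at Day 56 and every 8 weeks thereafter, the next draw is at Day 56 + 56 = Day 112, well after the window has closed.

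The objection is also right that the long courses are not the planned ones. The 1.8 Gy fraction appears only in the sample schedule in Table 3, and 49 days is a ceiling. They are permitted, not expected.

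Some stronger readings are tempting but not supported:
- A reader might infer that the standard course is left unmonitored at its end. It is not: it ends by Day 55.
- A reader might infer that every interrupted course can be miscounted. A related grade 3 toxicity that delays radiotherapy by more than seven days is already a DLT, so a later missed test does not change that patient's status. What remains is shorter interruptions, and longer ones not already counted.
- A reader might take weekly in Table 4 and bi-weekly in the Study Summary for two different schedules. Both name weeks 2, 4 and 6, as does the first footnote to Table 5. This is a clerical slip.

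**Conclusion.** The point holds for longer or interrupted courses only. The limits in Sections 4.9 and 7.1 can fall before the DLT window in Section 4.2.1 closes: by up to 4 days with 33 x 1.8 Gy, by 2 to 6 days with 49 days of temozolomide, and by up to 6 days when a 30 x 2 Gy course is interrupted for seven days. A longer interruption that is not itself a DLT pushes the end later still. In those days no scheduled blood test looks for a hematologic DLT, and the patient could be counted as DLT-free.

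This rests on Day 0 being the injection, weekday fractions, temozolomide starting with radiotherapy, and a laboratory test actually being done at Day 56, as Section 4.9 implies. The documents do not give the share of patients who would run past Day 56; it is probably small. The escalation probabilities in Table 10 are unaffected, because they take the true DLT rate as given. The amendment is worth making because it is cheap and protects the count on which the primary endpoint depends.

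**What to change.** In Sections 4.9 and 7.1, replace the Day 56 limit with *Day 56 or completion of RT/TMZ, whichever is later*. Schedule a complete blood count and chemistry at that time point, and carry it into Tables 4 and 5. In Section 4.2, state that a patient counts as DLT-free for Table 2 only once that result is available. Leave Table 10 as it is. The weekly/bi-weekly wording can be tidied in the same amendment.

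The cost is amendment text, a few routine blood draws, and a wait before the escalation decision of up to about 6 days past Day 56 for uninterrupted courses, longer for interrupted ones.
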